Activated Partial Thromboplastin Time (aPTT)	$\leq 1.5 \times$ institutional ULN unless subject is receiving anticoagulant therapy as long as PT or PTT is within therapeutic range of intended use of anticoagulants

^aCreatinine clearance should be calculated per institutional standard.

3.1.9 CT or MRI within 14 days prior of registration.

NOTE: Due to the fact that the screening MRI will not be used for response purposes, participants may be registered if screening CT or MRI is > 14 days of registration if prospective approval is received from Overall PI, [name] (for prospectively approved circumstances an eligibility exception will not need to be filed).

3.1.10 An interval of at least 4 weeks (to registration) between prior surgical resection or one week for stereotactic biopsy.

3.1.11 An interval of at least 12 weeks from the completion of radiation therapy to registration unless there is unequivocal histologic confirmation of tumor progression.

3.1.12 Participants must have recovered to grade 0 or 1 or pre-treatment baseline from clinically significant toxic effects of prior therapy (including but not limited to exceptions of alopecia, laboratory values listed per inclusion criteria, and lymphopenia which is common after therapy with temozolomide).

3.1.13 From registration, the following time periods must have elapsed: 5 half-lives from any investigational agent, 4 weeks from cytotoxic therapy (except 23 days for temozolomide and 6 weeks from nitrosoureas), 6 weeks from antibodies, or 4 weeks (or 5 half-lives, whichever is shorter) from other anti-tumor therapies (including vaccines). No wash-out period required from TTF.

3.1.14 Participants must have sufficient tissue from most recent surgery revealing glioblastoma or variants for submission following registration. The following amount of tissue is required:

- 1 formalin-fixed paraffin-embedded (FFPE) tumor tissue block

3.1.15 Patients with a prior or concurrent malignancy whose natural history or treatment does not have the potential to interfere with the safety or efficacy assessment of the trial are eligible.
NOTE: consultation with the Overall PI is highly recommended if enrollment of a patient with a prior or concurrent malignancy will be pursued.

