4.1 General Guidelines for DF/HCC Institutions

Institutions will register eligible participants in the Clinical Trial Management System (CTMS) OnCore. Registrations must occur prior to the initiation of protocol-specific therapy or intervention. Any participant not registered to the protocol before protocol therapy begins will be considered ineligible and registration will be denied.

An investigator will confirm eligibility criteria and a member of the study team will complete the ODQ protocol-specific eligibility checklist.

Following registration, participants may begin protocol therapy and/or intervention. Issues that would cause treatment delays should be discussed with the Overall Principal Investigator (PI). If

a participant does not receive protocol therapy following registration, the participant's participant must be taken off-study in the CTMS (OnCore) with an appropriate date and reason entered.

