5. TREATMENT PLAN

This is a pilot surgical trial to evaluate early immunologic pharmacodynamic parameters for the PD-1 checkpoint inhibitor, pembrolizumab (MK-3475), in patients with surgically accessible recurrent/progressive glioblastoma. The principle goal of this study is to understand, in surgically resectable recurrent/progressive GBM, if neoadjuvant pembrolizumab elicits a systemic immunologic response, a tumoral immunologic response and toxicity and if that response can be correlated with other non-invasive measures of pembrolizumab bioactivity (tumor, blood, imaging, and clinical outcomes). The study includes 2 stages, in the first stage (**Stage 1**), for optimal understanding of the effect of the drug on tumor tissue patients will be randomized in to Group A or Group B. In the second stage (**Stage 2**), additional patients will be enrolled to an expansion arm of Group A only to specifically study the effect of the drug on cell cycle/cancer proliferation related genetic signature.

Stage 1:

Groups A and B: Patients will be randomly assigned to either group A or B with a 1:1 randomization ratio prior to surgery. Patients in all groups will receive the study drug pembrolizumab after tumor resection. Only Group A will receive a single infusion of pembrolizumab of 200mg 14± 5 days prior to surgery (when scheduling, please keep in mind that the two pre-surgical plasma samples should be drawn greater than 10 days apart - see Table 6 for full details). Group B will not receive study drug prior to surgery. **This randomization scheme should not negatively impact study accrual and will provide an invaluable control cohort for PD evaluations.**

Group A: Neoadjuvant/adjuvant evaluation: Fifteen eligible patients will receive a single infusion of pembrolizumab of 200mg 14± 5 days prior to scheduled surgical resection for

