10.1 Anti-Tumor Effect Definitions

10.1.1 Evaluable for toxicity. All participants who receive at least one dose of study treatment will be evaluable for toxicity from the time of their first treatment.

10.1.2 Evaluable for objective response. Only those participants who have measurable disease present at baseline (obtained within 14 days of cycle 1, day 1) scan and have received at least one dose of therapy will be considered evaluable for response. These participants will have their response classified according to the definitions stated below. (Note: Participants who exhibit objective disease progression or die prior to the end of cycle 1 will also be considered evaluable.)

10.1.3 Measurable disease. Bi-dimensionally, contrast-enhancing, measurable lesions with clearly defined margins by CT or MRI scan, with a minimal diameter of 1 cm, and visible on 2 axial slices which are at least 5 mm apart with 0 mm skip. Measurement of tumor around a cyst or surgical cavity, if necessary, requires a minimum thickness of 3 mm. If there are too many measurable lesions to measure at each evaluation, the investigator must choose the largest two to be followed before a participant is entered on study. The remaining lesions will be considered non-measurable for the purpose of objective response determination. Unless progression is observed, objective response can only be determined when all measurable and non-measurable lesions are assessed.

10.1.4 Non-measurable evaluable disease. Unidimensionally measurable lesions, masses with margins not clearly defined, lesions with maximal diameter < 1cm.

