10.4 Evaluation of Best Response

The best overall response is the best response recorded from the start of the treatment until disease progression (taking as reference for progressive disease the smallest measurements recorded since the treatment started). If a response recorded at one scheduled MRI does not persist at the next regular scheduled MRI, the response will still be recorded based on the prior scan, but will be designated as a non-sustained response. If the response is sustained, i.e. still present on the subsequent MRI at least four weeks later, it will be recorded as a sustained response, lasting until the time of tumor progression. Participants without measurable disease may only achieve SD or PD as their best “response.”

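### For patients with too many lesions to follow, section 10.1.3 has the two target lesions chosen before the on-study resection, although the response reference is a post-surgery MRI

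*Combined protocol and SAP*

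**What the plan says.** Section 10.1.3 restricts the followed lesions, on the condition that they are too many to measure at every assessment: "the investigator must choose the largest two to be followed before a participant is entered on study". It times that choice before entry and treats the other lesions as non-measurable when objective response is determined.

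Entry comes before the operation. Section 4.1: "Registrations must occur prior to the initiation of protocol-specific therapy or intervention". Section 5, for Stage 1: "Patients will be randomly assigned to either group A or B with a 1:1 randomization ratio prior to surgery".

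Other sections place the response reference after surgery:
- The note to 3.1.9 allows an older screening scan with prior approval, and gives this reason: "Due to the fact that the screening MRI will not be used for response purposes".
- Section 1.1 starts six-weekly response imaging once the patient has recovered from surgery.
- Study calendar footnote ee concerns a post-surgery MRI in both groups, to be repeated if it lies more than 21 days from the start of post-surgery pembrolizumab.
- Section 10.1.2 counts as evaluable for response only participants with "measurable disease present at baseline (obtained within 14 days of cycle 1, day 1) scan" who have had at least one dose. Section 10.3 also sets a 14-day limit, counted back from the start of treatment.

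No section says that the followed lesions are chosen again after the resection.

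The reference for progression is stated twice. Section 10.2.3(a) uses best response, or baseline if there was no decrease. Section 10.4 has "taking as reference for progressive disease the smallest measurements recorded since the treatment started".

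**The concern.** For the patients to whom the rule applies, lesion choice and baseline measurement rest on different scans with a debulking operation between them. The largest lesions are plausible targets of that operation. If they are partly or wholly removed, the followed set may hold little or no tumour at baseline, while a residual lesion large enough to measure falls outside it.

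What is at stake is the RANO response classification and, through the progression date, PFS and the secondary endpoint PFS6 (12.2.4.1). Section 10.4 raises a related question, because treatment starts before surgery in Group A and after it in Group B.

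**Working it through.** The plan gives no figure to reproduce. The check compares sections, with day counts and percentage changes.

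**1. Can a pre-entry scan serve as the baseline?** Inputs for Group A:
- screening scan 0 to 14 days before registration (footnote v);
- first dose at or after registration; no limit on this gap was found, so it is taken as 0;
- surgery 14 ± 5 days after that dose, that is 9 to 19 days (section 5);
- first post-surgery dose 0 to 35 days after surgery (footnote x).

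Shortest time from pre-entry scan to surgery: 0 + 0 + 9 = 9 days. Longest time from that scan to the first post-surgery dose: 14 + 19 + 35 = 68 days, or more if there is a gap after registration or an older scan is approved under 3.1.9. If cycle 1, day 1 is the first post-surgery dose, a pre-entry scan meets the 14-day window of 10.1.2 only when that dose comes within 14 − 9 = 5 days of surgery. The pre-entry scan is therefore not a workable baseline, which agrees with 3.1.9. The lesion choice in 10.1.3 is tied to it all the same.

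**2. Effect on response.** Suppose the two chosen lesions are fully resected and a third, measurable in size, remains. Under 10.1.3 the third is non-measurable for response. The patient then has no measurable disease at baseline and is not evaluable under 10.1.2, or can reach only stable or progressive disease under 10.4.

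**3. Effect on progression.** In the same illustration the third lesion grows from 1.0 to 2.0 cm², a change of (2.0 − 1.0)/1.0 = +100%.
- If the sum covers only the chosen two, it stays at 0. A percentage change from 0 is undefined, and 10.2.3(a) is not met.
- If the sum covers all enhancing lesions, it rises from 1.0 to 2.0 cm². That is +100% against the 25% threshold, so 10.2.3(a) is met.

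Criterion (b) does not settle it, because the lesion is not new, and 10.2.3 has no separate criterion for growth of non-measurable disease. Two sites could classify the same scans differently.

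**4. The reference in 10.4.** Take an early post-operative scan on day 2 and first post-surgery dosing on day 30 (illustrative). The gap is 30 − 2 = 28 days, more than 21, so footnote ee requires a repeat. Let the scans read 2.0 and then 3.0 cm²: (3.0 − 2.0)/2.0 = +50%.
- Under 10.4, with treatment start read as the pre-surgery dose, 2.0 cm² is the reference in Group A and the repeat scan is progression. In Group B treatment has not started, and 3.0 cm² is the baseline.
- Under 10.2.3(a), with the repeat scan as baseline, neither patient has progressed.

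**5. Baseline windows.** If the post-surgery MRI precedes the first post-surgery dose by more than 14 and up to 21 days, it satisfies footnote ee but not 10.1.2 or, if treatment start is read as that dose, 10.3.

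**The case against.** The strongest reply is that the protocol already puts the baseline after surgery. The screening MRI is set aside for response, a post-surgery MRI exists in both groups, and 10.1.3 itself covers measuring tumour around a surgical cavity. A sensible investigator would choose lesions on that scan. This stands in part. Those provisions fix which scan is the baseline, but not which lesions are followed on it, and the one sentence that does so points to the earlier time.

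A reader might infer more than the text supports:
- *That every participant's followed lesions are fixed before surgery.* The rule applies only when there are too many lesions to measure.
- *That the chosen lesions are gone, so the wrong ones are followed.* Section 3.1.16 expects at least 400 mg of tumour to be resectable, not removal of every large lesion. The zero sum above is an assumption.
- *That growth of a residual lesion cannot count as progression.* The non-measurable label is limited to determining objective response. Section 10.2.3(a) refers to enhancing lesions without confining the sum to the chosen two, and Table 7 does not confine it either. Clinical deterioration, and death or decline that prevents evaluation, remain routes to progression. Section 10.5 has investigators consider non-target lesions, though only in the exploratory iRANO assessment.
- *That progression is easier to reach in Group A.* This requires reading treatment start in 10.4 as the pre-surgery dose and letting a parenthesis in a section on best response override 10.2.3(a).

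Each of these limits stands. What remains is a conflict of timing and two ambiguities.

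**Conclusion.** The point holds as a wording conflict that should be corrected. In patients with too many lesions to measure, 10.1.3 ties lesion choice to a time before the resection, other sections put the response reference after it, and no step links the two. Applied literally, the rule can cost a patient response evaluability or limit best response to stable or progressive disease, and it leaves progression by residual tumour open to two readings.

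The difference between 10.4 and 10.2.3(a) is a possible inconsistency and not a demonstrated bias between groups. PFS6 is analysed with the groups pooled (12.2.6.1), and the between-group PFS comparison is exploratory (12.2.6.3). TIL density, the cell cycle signature and safety do not depend on lesion choice.

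The size cannot be given: the documents report neither how many patients have multiple lesions nor how often the largest are resected. The conclusion assumes that entry means registration and that cycle 1, day 1 is the first post-surgery dose.

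**What to change.** 1. In 10.1.3, replace "to be followed before a participant is entered on study" with wording such as: *to be followed, selected on the post-surgery baseline MRI before the first post-surgery pembrolizumab dose*.
2. In 10.4, word the progression reference to agree with 10.2.3(a): the smallest measurement from that post-surgery baseline MRI onward, in both groups.
3. Reconcile the 14-day window (10.1.2, 10.3) with the 21-day window (footnote ee).

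Items 1 and 2 use an MRI that the calendar already provides for, so they need no new scan. Depending on how item 3 is settled, some post-surgery scans might need repeating. The changes require a protocol amendment. Section 1.1 reports that Stage 1 data have already had an interim analysis, so Stage 1 multi-lesion cases may need their target-lesion list and progression reference checked, and possibly scans re-read, before PFS and PFS6 are pooled with Stage 2.

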10.2 Response/Progression Categories

10.2.1 Complete response (CR). All of the following criteria must be met:

- Complete disappearance of all enhancing measurable and non-measurable disease sustained for at least 4 weeks. In the absence of a confirming scan 4 weeks later, this scan will be considered only stable disease.
- No new lesions.
- All measurable and non-measurable lesions must be assessed using the same techniques as baseline.
- Participants must be on no steroids or on physiologic replacement doses only.
- Stable or improved non-enhancing (T2/FLAIR) lesions

- f) Stable or improved clinically, for clinical signs and symptoms present at baseline and recorded to be disease related

Participants with non-measurable disease cannot have a complete response. The best response possible is stable disease.

10.2.2 Partial response (PR). All of the following criteria must be met:

- a) Greater than or equal to 50% decrease compared to baseline in the sum of products of perpendicular diameters of all measurable enhancing lesions sustained for at least 4 weeks. In the absence of a confirming scan 4 weeks later, this scan will be considered only stable disease.
- b) No progression of non-measurable disease.
- c) No new lesions.
- d) All measurable and non-measurable lesions must be assessed using the same techniques as baseline.
- e) The steroid dose at the time of the scan evaluation should be no greater than the dose at time of baseline scan.
- f) Stable or improved non-enhancing (T2/FLAIR) lesions on same or lower dose of corticosteroids compared to baseline scan.
- g) Stable or improved, for clinical signs and symptoms present at baseline and recorded to be disease related clinically.

Participants with non-measurable disease cannot have a partial response. The best response possible is stable disease.

10.2.3 Progressive disease (PD). Any of the following criterion must be met:

- a) > 25% increase in sum of the products of perpendicular diameters of enhancing lesions (over best response or baseline if no decrease) on stable or increasing doses of corticosteroids
- b) Any new enhancing measurable lesion
- c) Clear clinical deterioration not attributable to other causes apart from the tumor (e.g. seizures, medication side effects, complications of therapy, cerebrovascular events, infection, etc.). The definition of clinical deterioration is left to the discretion of the investigator but it is recommended that a decline in the Karnofsky Performance Score (KPS) from 100 or 90 to 70 or less, a decline in KPS of at least 20 from 80 or less, or a decline in KPS from any baseline to 50 or less, for at least 7 days, be considered neurologic deterioration, unless attributable to co-morbid events or changes in corticosteroid dose.
- d) Failure to return for evaluation due to death or deteriorating condition

10.2.4 Stable disease (SD). All of the following criteria must be met:

- a) Does not qualify for CR, PR, or progression.
- b) All measurable and non-measurable sites must be assessed using the same techniques as baseline.
- c) Stable clinically.

10.2.5 Unknown response status. Progressive disease has not been documented and one or more measurable or non-measurable lesions have not been assessed.

The RANO Response Criteria to be used in this study are summarized in Table 7.

Table 7 Summary of the RANO Response Criteria

	CR	PR	SD	PD#
T1-Gd +	None	$\geq 50\%$ decrease	$<50\%$ decrease- $<25\%$ increase	$\geq 25\%$ increase*
T2/FLAIR	Stable or decrease	Stable or decrease	NA	NA
New Lesion	None	None	None	Present*
Corticosteroids	None	Stable or decrease	Stable or decrease	Stable or increasing
Clinical Status	Stable or increase	Stable or increase	Stable or increase	Decrease*
Requirement for Response	All	All	All	Any*

CR=complete response; PR=partial response; SD=stable disease; PD=progressive disease;
NA= not applicable

#: Progression occurs when any of the criteria with * is present

Increase in corticosteroids alone will not be taken into account in determining progression in the absence of persistent clinical deterioration

Of note, patients who require increased corticosteroids within two weeks of MRI assessment (relative to the dose taken at the time of the prior assessment) cannot be classified as CR, PR or SD and should be classified as non-evaluable at that time point. Conversely, patients who decrease corticosteroids within two weeks of MRI assessment (relative to the dose taken at the time of the prior assessment) cannot be classified as PD and should be classified as non-evaluable.

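### As worded, the closing sentences of 10.2.1 and 10.2.2 cap patients who have both measurable and non-measurable lesions at stable disease, against the CR and PR criteria they follow

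*Combined protocol and SAP*

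**What the plan says.** Section 10.1.2 defines who is evaluable for objective response: "Only those participants who have measurable disease present at baseline", with at least one dose received. Of this group it says: "These participants will have their response classified according to the definitions stated below". It does not exclude patients who also have non-measurable lesions.

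Section 10.1.3 covers the case where there are too many measurable lesions to measure each time. The largest two are followed, and "The remaining lesions will be considered non-measurable for the purpose of objective response determination". Section 10.1.4 counts as non-measurable any lesion under 1 cm, any lesion measurable in one dimension only, and any mass without clear margins.

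Section 10.2.1(a) requires, for complete response, "Complete disappearance of all enhancing measurable and non-measurable disease sustained for at least 4 weeks". The subsection closes: "Participants with non-measurable disease cannot have a complete response. The best response possible is stable disease".

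Section 10.2.2(b) requires, for partial response, "No progression of non-measurable disease". The subsection closes: "Participants with non-measurable disease cannot have a partial response. The best response possible is stable disease".

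Section 10.4 sets the ceiling on best overall response for a different group: "Participants without measurable disease may only achieve SD or PD as their best" response. Table 7, which summarises the RANO categories, contains no ceiling tied to non-measurable disease.

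**The concern.** The two closing sentences name patients who have non-measurable disease, not patients who have nothing else. A site that applies the words as they stand would code a mixed-disease responder as stable. A site that follows the lettered criteria would code the same patient as a partial or complete response. Central imaging review takes place only on request (10.6), so nothing in the plan ensures that such differences are found.

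Section 1.1 names response rate by RANO as an efficacy endpoint. Objectives 1.4.1.1 and 1.4.1.6 relate TIL density, clonality and T-cell expansion to clinical response, and 8.2 and 8.4 list ORR among the outcomes for biomarker correlation. Responders coded as stable would lower the response rate and put patients in the wrong outcome category in those analyses.

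**Working it through.** The plan gives no figure to reproduce. The check is one of logic: classify each type of baseline disease under each provision and see where they part.

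| Baseline disease | Closing sentences of 10.2.1 and 10.2.2, read literally | Criteria 10.2.1(a), 10.2.2(b) | Ceiling in 10.4 | Consistent? |
|---|---|---|---|---|
| Measurable only | no cap | CR or PR possible | no cap | yes |
| Non-measurable only | SD at best | not response-evaluable (10.1.2) | SD at best | yes |
| Measurable plus non-measurable | SD at best | CR or PR possible | no cap | **no** |
| Several measurable lesions, some set aside under 10.1.3 | SD at best | CR or PR possible | no cap | **no** |

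**Conflict inside 10.2.** New lesions have their own criterion in both definitions: 10.2.1(b) for CR and 10.2.2(c) for PR. So 10.2.2(b) can only concern non-measurable lesions already present at baseline. If every patient with such a lesion is barred from PR, 10.2.2(b) never applies to anyone. In the same way, the non-measurable part of 10.2.1(a) would have no patient to apply to.

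**Where the cap acts.** Section 10.1.2 already keeps patients without measurable disease out of the response-evaluable set. Within that set, the literal cap can therefore reach only mixed-disease patients, the group that 10.4 leaves uncapped.

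**A worked record.** Take one clearly bounded lesion of 20 × 20 mm that shrinks to 10 × 10 mm, confirmed at four weeks. Steroids, T2/FLAIR and clinical status are stable and there is no new lesion.

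- Product of diameters: 20 × 20 = 400 mm² at baseline and 10 × 10 = 100 mm² later.
- Decrease: (400 − 100) / 400 = 75%, above the 50% needed for PR. The result is PR.
- Now add a 6 mm focus that stays stable. It is non-measurable under 10.1.4 because it is under 1 cm. Criteria (a) to (g) of 10.2.2 are still met, so the lettered criteria give PR. The closing sentence gives SD.

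**What the coding does not touch.** Progression under 10.2.3 depends on growth, new lesions, clinical decline or failure to return. Section 10.4 takes the smallest recorded measurements as the reference for growth, not the response category. Coding SD in place of PR therefore neither creates nor removes a progression event, and PFS6 (12.2.4.1) is unchanged. TIL density, the cell-cycle signature and safety do not use response category at all.

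**Size.** If a share m of true responders has mixed disease, the response rate under the literal rule is (1 − m) times the rate under the lettered criteria. The documents give neither m nor an expected response rate, so m could lie anywhere from 0 to 1. For scale only: 30 + 20 = 50 evaluable patients are planned. If all 50 were response-evaluable, each recoded patient would move the rate by 1/50 = 2 percentage points, and by more if fewer were evaluable.

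**The case against.** The strongest reply is that the text can be read sensibly as it stands. A patient with non-measurable disease may mean one whose disease is non-measurable, as opposed to the group in 10.1.2. That reading fits 10.2.1(a), 10.2.2(b), Table 7 and 10.4, and it is very probably what was intended. This stands as an account of intent. It does not remove the defect, because the reader has to override the express words of an outcome definition to reach it.

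Three stronger readings are tempting, and the documents do not support them.

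- **That any patient with three or more measurable lesions is capped.** Section 10.1.3 sets lesions aside only when there are too many to measure at each evaluation, and gives no number. Three lesions do not trigger the rule by themselves. The cap follows only where the rule is invoked.
- **That 10.4 flatly contradicts 10.2.** Section 10.4 caps one group and does not say that everyone else may reach CR or PR. The tension is by implication. The direct conflict is within 10.2.1 and 10.2.2.
- **That the response rate would fall by a stated amount.** One could assume a true rate of 15%, equal response rates in mixed and other disease, and a mixed share of 20% or 40%. The literal rates are then 0.15 × 0.8 = 12% and 0.15 × 0.6 = 9%. Every input is assumed, so these figures illustrate the formula and are not evidence about this trial.

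It is also fair to say that the stake is modest. Apart from the mention in 1.1, no objective estimates response rate. Section 12.2.4.1 measures efficacy by PFS6, 12.2.6.1 contains no response-rate analysis, and the Cox models in 12.2.6.3 use PFS and OS. If the baseline scan for response is the post-resection scan, few patients may have measurable disease. The documents do not say how many.

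**Conclusion.** The concern holds as an error of wording in a classification rule. Followed literally, the closing sentences of 10.2.1 and 10.2.2 code mixed-disease responders as stable disease, against criteria 10.2.1(a) and 10.2.2(b) and out of line with 10.4. The same happens to patients whose extra lesions are set aside under 10.1.3.

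The consequence is limited to the RANO response rate in 1.1 and the exploratory correlations with response or ORR. Its size is unknown. It depends on the share of responders with mixed disease and on whether sites apply the literal words, and the documents give neither.

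A reader might infer that the trial deliberately denies response to all mixed-disease patients, or that its main conclusions are at risk. Neither follows: the lettered criteria and 10.4 point to a narrower intent, and neither the primary endpoints nor PFS6 uses the distinction between response and stable disease.

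**What to change.** Reword the closing sentence of 10.2.1 to: *Participants with only non-measurable disease (no measurable lesion at baseline) cannot have a complete response.* Make the same change in 10.2.2 for partial response. Both then match 10.4, and all four rows of the table above agree. No separate statement about 10.1.3 is needed, because a patient whose extra lesions are set aside still has measurable lesions at baseline.

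The cost is a short edit to two sentences at the next amendment, with no new data, visits or assays. Response assessments already recorded as stable disease in patients with both lesion types should be checked once against the reworded rule before any response rate or response correlation is reported.
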